4.2.7. Progression-free Survival

Progression-free Survival (PFS) is defined as the time (months) from the start of study treatment from Cycle 1 in continuous cycle (i.e. not from the date of single oral dose from the PK week for the dose escalation part) to disease progression, or relapse, or death due to any cause, whichever occurs first. More specifically, PFS will be determined using all the assessment data up until the last evaluable visit prior to or on the date of

- (i) disease progression (at least 2 cycles of study drug should be administered to determine PD) or relapse as defined by 2017 ELN criteria for AML patients, or
- (ii) withdrawal of consent; or lost to follow-up, or
- (iii) receiving subsequent anti-tumor therapy, whichever is earlier.

Patients without report of PD or death due to any cause at the time of analysis are censored as described in [Table 7](#) below.

Table 7 Outcome and Event or Censoring Dates for PFS

Rule	Situation	Date of Progression or Censoring	Outcome
------	-----------	----------------------------------	---------

1	PD/relapse documented between schedule tumor assessment visit or after one missing tumor assessment visit	Date of first documented disease progression/relapse	Event
2	Death without PD/relapse between schedule tumor assessment visit or death on or before the second scheduled visit or death after one missing tumor assessment visit	Date of death	Event
3	No baseline or post-baseline tumor assessments available and subject dose not die	Date of first administration of study treatment	Censored
4	No death or PD/relapse by the time of data cut-off for final analysis	Date of last adequate tumor assessment prior to or on analysis data cutoff date	Censored
5	Early discontinuation (lost to follow-up or withdrawal of consent) of study without death or PD/relapse	Date of last adequate tumor assessment	Censored
6	Subsequent anti-tumor therapy started prior to PD/relapse or death	Date of last adequate assessment prior to or on date of initiation of subsequent therapy visit	Censored
7	PD/relapse or death after missed or inadequate two or more consecutive tumor assessment visits	Date of last adequate tumor assessment prior to missed visits or date of first administration of study treatment (if no post-baseline tumor assessment)	Censored

Note: An adequate tumor assessment is defined as an assessment where the Investigator determined response is CRMRD-, CR, CRh, CRi, MLFS, PR, SD, and PD/relapse. If PD/relapse and subsequent anti-cancer therapy occur on the same day, will assume that the progression/relapse was documented first, e.g. outcome is progression/relapse and the date is the date of the assessment of progression/relapse.

Note: The same algorithm for determination of one and two/more consecutive missing or inadequate assessments can be found in [Section 4.2.3](#).

PFS (months) is calculated as (date of event or censoring as per rules in [Table 7](#) – date of first administration of study treatment from Cycle 1 + 1)/30.4375. Reasons for censoring are included in [Table 8](#) following the hierarchy.

Table 8 PFS Censoring Reasons and Hierarchy

Hierarchy	Condition	Censoring Reason
1	No baseline or post-baseline tumor assessments available and subject dose not die	No baseline or post-baseline tumor assessments
2	Subsequent anti-tumor therapy started prior to PD/relapse or death	Subsequent anti-tumor therapy started prior to PD/relapse or death
4	PD/relapse or death after missed or inadequate two or more consecutive tumor assessment visits	Missed or inadequate two or more consecutive tumor assessment visits
5	Drops out before end of study, no progression/relapse or death, lost to follow-up	No death or PD/relapse, lost to follow-up
6	Drops out before end of study, no progression/relapse or death, withdrawal by subject from the study	No death or PD/relapse, withdrawal by subject
7	No death or PD/relapse by the time of data cut-off for the analysis	No death or PD/relapse by the time of data cut-off for the analysis

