2.3 Benefit/Risk Assessment

2.3.1 Benefit-Risk Assessment

The patients to be enrolled in this study will be those with advanced, relapsed, refractory, or resistant hematological malignancies and, therefore, have an unmet medical need.

For patients with refractory AML, the median overall survival (OS) is approximately 1.5 months with only 8% one-year survival (Gale 2008, Giles 2005). National Comprehensive Cancer Network (NCCN) and European Society for Medical Oncology (ESMO) practice guidelines recommend considering clinical trial for patients with primary refractory AML (NCCN-AML 2021, Heuser 2020). In the event that no clinical trial is available, then the intent of a second salvage chemotherapy in these patients, however, is only supportive at best. Therefore, patients with AML who have received at least 2 prior lines of therapy do not have a viable

treatment option available. Additionally, AML patients who fail IDH inhibitor therapies do not have any standard treatment options available, making them a population with very high unmet need ([NCCN-AML 2021](#)).

High-risk MDS (HR-MDS) carries a major risk of progression to AML and short survival. There are no standard treatment options for patients with relapsed or refractory HR-MDS. Patients ineligible for allo-HSCT have no approved second-line treatment options after failure of an approved hypomethylating agent (HMA), and clinical trials are the recommended option as per NCCN and ESMO guidelines ([NCCN-MDS 2021](#), [ELN 2017](#), [Fenaux 2020](#)).

Similarly, ESMO and NCCN practice guidelines recommend considering clinical trial for patients with relapsed or refractory AITL because of the poor survival rate with available single agent palliative therapy options ([NCCN-MDS 2021](#), [NCCN-PTCL 2021](#), [d'Amore 2015](#)).

HMPL-306 is a dual inhibitor of IDH1 and IDH2, which, in preclinical studies, has demonstrated similar efficacy to single target IDH inhibitors (ivosidenib and enasidenib), and may have similar benefit to other IDH1 and/or IDH2 inhibitors in the same class. Preclinical studies, including toxicology studies, indicate that HMPL-306 is well tolerated. Additionally, there are no approved therapies for the treatment of hematological malignancies that have been previously treated with an mIDH1 or mIDH2 inhibitor, thus providing a potential treatment option in an area of unmet medical need.

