6.2 Discontinuation or Withdrawal

6.2.1 Discontinuation of Treatment

6.2.1.1 Permanent Discontinuation of Treatment

The investigator has the right to discontinue a patient from the study for any medical condition that the investigator or sponsor determines is in the best interest of the patient; reasons may include non-compliance (eg, missed doses, visits) or pregnancy.

Any patient who discontinues treatment should be encouraged to return to the study site for an EOT Visit and continue with the remaining study visits. The primary reason(s) for discontinuation must be recorded on appropriate CRF.

Patients must be discontinued from treatment for disease progression, withdrawal of consent, intolerable toxicity, as outlined in [Table 8](#), [Table 9](#), and [Table 10](#), repeated non-compliance or poor compliance, commencement of other antitumor treatment during the study, pregnancy, loss to follow-up, termination of the study by the sponsor, death, or end of the study.

Patients may receive a maximum of 6 cycles of therapy unless the following are met:

- Patients with AML must have a partial response (PR) or better based on the 2017 ELN criteria ([Appendix 8](#)).
- Patients with HR-MDS must have a hematological response or better based on the IWG Criteria ([Appendix 12](#))
- Patients with AITL must have a stable disease (SD) or better based on the Lugano Classification ([Appendix 9](#)).

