9.2.7 Efficacy Analysis

Tumor assessment for patients with AML, HR-MDS, or AITL will be evaluated by the investigator according to the specific guidelines outlined in Section 9.2.7.1. However, the efficacy analysis will only be conducted for AML patients; for patients with HR-MDS or AITL, if enrolled, the tumor assessment data will be listed.

The following efficacy endpoints will be derived and analyzed using the safety analysis set for patients with AML:

- OS: defined as the time from the start of the study drug until death from any cause.
- Progression-free survival (PFS): defined as the time from the start of study treatment to disease progression, or death due to any cause, whichever occurs first.
- Baseline transfusion dependence: transfusions of red blood cells (RBCs) or platelets within 28 days prior to the first dose of treatment.
- Post-baseline transfusion independence (summarized through the following 2 ways):
 - No RBC or platelet transfusion for at least ≥ 4 weeks during treatment period; or
 - No RBC or platelet transfusion for at least ≥ 8 weeks during treatment period.

Patients with AML treated at the RP2D from Part 1 will be included in the data summary of the cohort in Part 2, unless otherwise specified. A patient data listing will be prepared for all patients.

Tumor response endpoints as defined in Section 9.2.7.1 (eg, best overall response, objective response rate [ORR], clinical benefit rate [CBR], and duration of response [DoR]) will be analyzed using the safety analysis set. For binary response endpoints such as ORR and CBR, the estimate and its 95% CI will be calculated using the Clopper-Pearson method for each cohort. The response (efficacy) evaluable analysis set will be used to conduct sensitivity analysis for tumor response.

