4.2. Efficacy Endpoints

4.2.1. Best Overall Response

Assessment of anti-tumor response for patients with AML will be conducted according to 2017 European Leukemia Net (ELN) criteria (Döhner et al, 2017). Best overall response (BOR) is defined as the best response during the anti-tumor evaluation period, which will be determined using time point responses (TPRs) from date of the first dose of study treatment from Cycle 1 in continuous cycle (i.e. not from the date of single oral dose from the PK week for the dose escalation part) up until the last evaluable TPR prior to or on the date of (i) disease progression (at least 2 cycles of study drug should be administered to determine PD) / relapse according to the 2017 ELN criteria, or death; or (ii) withdrawal of consent or lost to follow-up; or (iii) receiving subsequent anti-cancer therapy, whichever is earlier.

The hierarchical order of these response categories is complete response with negative minimal residual disease (CR_{MRD-}) > complete response (CR) > complete response with partial hematological recovery (CRh) > complete response with incomplete count (CRI) > morphologically leukemia-free state (MLFS) > partial response (PR) > stable disease (SD) > progressive disease (PD) > NE (not evaluable), where CR_{MRD-} , CR and CRI are based on investigator assessment of response, and CRh will be derived from relevant data including investigator-collected bone marrow and hematology data by medical team as external file, as CRh is not defined in ELN 2017. This order will be used to derive the BOR. For example, a patient who has 4 anti-tumor assessments during the anti-tumor evaluation period with response being MLFS, PR, SD, and PD respectively, then the BOR for this patient will be MLFS.

Of note, for the BOR being SD, it is expected that the duration of SD lasts for at least 3 cycles, for example, if a patient only has one tumor assessment at 2 cycles with response being SD, then, the BOR for this patient will be NE instead. For the BOR being PD, at least 2 cycles of study drug should be administered, for example, if a patient only has one tumor assessment at 1 cycle of study drug with response being PD, then, the BOR for this patient will be NE instead.

Moreover, subjects who do not have post-dose tumor assessment, but have clinical progression as noted by the investigator or have died due to any cause before their second post-dose tumor assessment, BOR will be PD.

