For patients whose BOR is 'NE', reasons for NE will be summarized as followings:

- All post-baseline overall responses are NE / No baseline or post-baseline assessments;
- Initiation of subsequent anti-tumor therapy prior to the first post-baseline tumor assessment;
- SD lasts less than 3 cycles;
- Less than 2 cycles of study drug to determine PD.

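### The SAP's 2-cycle minimum for progression conflicts with the protocol and with SAP Table 7, and can turn a documented early progression into a not-evaluable best response and a censored or later-dated PFS time

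*SAP*

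**What the plan says.** - **Protocol 9.2.7** has PFS "defined as the time from the start of study treatment to disease progression, or death due to any cause, whichever occurs first". No minimum exposure is attached.
- **SAP 4.2.7** lets PFS run to "disease progression (at least 2 cycles of study drug should be administered to determine PD) or relapse as defined by 2017 ELN criteria".
- **SAP 4.2.1** carries the same condition into best overall response (BOR). A patient who "only has one tumor assessment at 1 cycle of study drug with response being PD, then, the BOR for this patient will be NE" (not evaluable), and the listed reasons for NE include "Less than 2 cycles of study drug to determine PD".
- **SAP 4.2.1** also says that patients with no post-dose assessment who "have clinical progression as noted by the investigator or have died due to any cause before their second post-dose tumor assessment, BOR will be PD".
- **SAP Table 7** makes documented progression an event on its first date (Rule 1) and death an event (Rule 2). It censors at cut-off (Rule 4), on leaving the study (Rule 5), at new anti-tumor therapy (Rule 6), and when the event follows two or more missed assessments (Rule 7). None of these rules mentions 2 cycles. The note below the table counts an assessment of progressive disease (PD) as adequate.
- **Protocol 6.2.1.1**: "Patients must be discontinued from treatment for disease progression". Under 6.1.19, tumor assessments go on only for patients who stopped for another reason, while survival follow-up covers everyone.
- **SAP Section 7**, the list of changes from the protocol, does not mention the 2-cycle condition.

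**The concern.** The condition asks for exposure that the protocol stops the patient from receiving. Someone taken off drug for a progression documented in week 5 will never reach 2 cycles and, having stopped for progression, has no further scheduled tumor assessments. Under the 2-cycle text that progression is not recognised as PD for BOR or PFS, and what happens next decides whether PFS is censored or dated later. Censoring that follows from having progressed is informative.

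The SAP also does not settle which rule governs. Section 4.2.7 carries the condition and Table 7 Rule 1 does not, so two programmers could derive different PFS from the same data. PFS and BOR are named secondary endpoints, and efficacy is reported by dose level, where the planned minimum is 3 patients. One reclassified patient can be visible in such a group.

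**Working it through.** **1. The plan's own numbers.** For an assessment before Day 106, SAP 4.2.3 sets the gap for two missed visits at 2 × (8 × 7 + 7) = 126 days, which reproduces. Two cycles are 2 × 28 = 56 daily doses. The first scheduled post-baseline assessment, C3D1, is Day 57, with a window of ±7 days (Days 50 to 64). By the start of Day 50 only 49 of 56 doses have been given. Whether an in-window visit on Days 50 to 55 meets the condition therefore depends on whether cycles must be started or completed, which the SAP does not say. The documents give no figure for the effect of the rule.

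**2. Where an earlier progression can be documented.** Protocol 6.1.10.3 allows extra marrow examinations at the investigator's discretion and requires one at the end-of-treatment visit. The schedules of events also place tumor evaluation there.

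**3. Tracing one patient.** PD is documented on Day 36 and drug is stopped for it.

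| What follows | PFS under the 2-cycle text | PFS under Rule 1 alone |
|---|---|---|
| New therapy on a later day | Censored (Rule 6), possibly on Day 36 itself, since a PD assessment is adequate | Event, Day 36 |
| Alive at cut-off, or leaves the study | Censored (Rules 4, 5) | Event, Day 36 |
| Death less than 126 days after Day 36, no new therapy | Event on the date of death (Rule 2) | Event, Day 36 |
| Death 126 days or more after Day 36, no new therapy | Censored (Rule 7) | Event, Day 36 |

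**4. Best response.** The same patient, if alive with only that assessment, has BOR = NE. If the end-of-treatment marrow had been skipped and clinical progression noted instead, BOR would be PD. Doing the required examination changes PD to NE. The part of that exception about death refers to a second post-dose assessment, so it may also make BOR = PD for an early progressor who dies; the wording is unclear.

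**5. Size if censored.** Assume that a share e of patients has an early PD, all censored before any later event, and a share m has a later event by 3 months, with no other censoring. Then 3-month PFS is 1 − e − m if early PD counts and (1 − e − m)/(1 − e) if it is censored. With m = 30%:

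- e = 10%: 60% against 0.6/0.9 = 66.7%
- e = 20%: 50% against 0.5/0.8 = 62.5%
- e = 30%: 40% against 0.4/0.7 = 57.1%

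**6. Size if delayed.** Take 10 constructed patients: early PD on Days 29, 36 and 43, other events on Days 57, 57, 113, 113, 169, 253 and 253. The median is read as the first day on which the Kaplan-Meier curve is at or below 50%.

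- Early PDs counted: the curve reaches 5/10 on Day 57; median 57 days.
- Early PDs censored: 5/7 = 71.4% after Day 57 and 3/7 = 42.9% after Day 113; median 113 days.
- Those three die 45 days later (Days 74, 81, 88) and count as deaths: 8/10 after Day 57 and 5/10 after Day 88; median 88 days.

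**7. Endpoints that do not move.** NE and PD are both non-responses in the same denominator, so ORR and CBR on the efficacy set stay the same. OS uses death only. EFS Table 4 Rule 4 already counts stopping before 24 weeks without CR as an event at first dose.

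**The case against.** The strongest reply is that Table 7 already handles these patients. SAP 4.2.7 sends to censoring only those with no report of progression or death, an early progressor has such a report, and Rule 1 counts it on its own date. That reading is available, but it leaves the 2-cycle clause in 4.2.7 with no effect on PFS and does nothing for BOR, where NE is explicit. The contradiction stands.

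A reader might infer that early progressions can never count and all become censored times. The documents do not support that. Apart from Rule 1, Rule 2 keeps death as an event, and survival follow-up covers every patient. Protocol 2.3.1 says that in refractory AML "the median overall survival (OS) is approximately 1.5 months with only 8% one-year survival". If that survival applied from the date of PD, with no new therapy, death within 126 days would have probability 1 − 0.5^(126/45.66) = 85% (exponential) or 73% (Weibull through both stated points). At assumed medians of 3 or 6 months it would be 62% or 38%. Without new therapy, many of these patients would have delayed events.

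A reader might also take the 1.5 months as a progression rate and derive a large 8-week PFS bias. That figure is overall survival in refractory AML. It counts deaths, which the rule leaves alone, and nothing in the documents says what share of early failures are documented progressions. The first scheduled assessment comes after 2 cycles, so mainly unscheduled and end-of-treatment assessments are exposed.

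Appendix 8 notes that a blast rise under IDH inhibition need not be progression. That is a fair reason for caution, most clearly where drug continues and the patient is reassessed. It is weaker where treatment was stopped for progression. It is also true that nothing is tested, that the primary endpoints are safety and MTD/RP2D, and that expansion enrolled one patient, who is merged into Cohort 8 (SAP 5.1.1). The harm is to descriptive estimates.

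**Conclusion.** The point holds in this form: the 2-cycle condition is an unlisted departure from the protocol, conflicts with Table 7 Rule 1, and cannot be met by a patient stopped for progression in cycle 1 or 2. Followed as written, it turns that patient's BOR into NE and either censors PFS or moves the event to death, both in the favourable direction.

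The size is unknown, because the number of early documented progressions is not given. The gain of 6.7 to 17.1 percentage points in 3-month PFS rests on an assumed 10% to 30% affected, all censored, and 30% with later events. Where deaths intervene the effect is a delay, as in step 6. It should be corrected before database lock, since PFS and BOR are secondary endpoints and the correction is cheap.

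**What to change.** 1. In SAP 4.2.1, its NE reasons, 4.2.7 and Table 7 Rule 1, replace the condition with: *An investigator-documented PD before 2 cycles is PD for BOR and a PFS event on its first documented date if study drug is stopped for progression, other anti-tumor therapy starts, or the patient dies with no later non-PD assessment. It is disregarded only if study drug continued and the next adequate assessment is not PD.*
2. Define 2 cycles administered: started or completed, how dose holds count, and how the ±7-day C3D1 window is treated.
3. Keep the present 2-cycle rule as a sensitivity analysis.
4. List the rule in SAP Section 7.
5. Reconcile protocol 6.2.1.1, which makes progression a mandatory stop, with protocol 8.6.7, which leaves a continuation decision to the investigator in consultation with the sponsor. The analysis rule above takes no position on which should apply.

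The cost is SAP wording and programming. Discontinuation reasons, assessment dates, later therapy and deaths are already collected. The downside is that PFS may look less favourable.

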4.2.8. Transfusion Dependence

Baseline transfusion dependence (TD) is defined as receipt of any transfusions of red blood cells (RBCs) or platelets within 28 days prior to the first dose of stud drug administration. The baseline TD for RBCs is defined as receipt of any transfusions of RBCs within 28 days prior to the first dose of stud drug administration, and baseline TD for platelets is defined as receipt of any transfusions of platelets within 28 days prior to the first dose of stud drug administration.

Post-baseline transfusion independence (TI) is defined as the absence of RBC and platelet transfusions for a prespecified time during treatment period which is defined from the first dose of study drug administration from Cycle 1 in continuous cycle to 30 days after the last dose date or prior to the start of a subsequent anti-tumor therapy (whichever comes first). Two post-baseline TI overall and for its components will be derived based on the pre-specified time.

- Post-baseline TI-4 is defined to have no RBC or platelet transfusion for at least ≥ 4 weeks during treatment period.
- Post-baseline TI-8 is defined to have no RBC or platelet transfusion for at least ≥ 8 weeks during treatment period.
- Post-baseline TI-4 for RBC is defined to have no RBC transfusion for at least ≥ 4 weeks during treatment period.
- Post-baseline TI-8 for RBC is defined to have no RBC transfusion for at least ≥ 8 weeks during treatment period.
- Post-baseline TI-4 for platelet is defined to have no platelet transfusion for at least ≥ 4 weeks during treatment period.
- Post-baseline TI-8 for platelet is defined to have no platelet transfusion for at least ≥ 8 weeks during treatment period.

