4.1.1 Part 1 (Dose Escalation)

The first part of the study is dose escalation, where cohorts of patients will receive ascending oral doses of HMPL-306 to determine MTD and/or the recommended phase 2 dose (RP2D). The modified toxicity probability interval-2 (mTPI-2) ([Greenberg 2012](#), [Guo 2017](#)) design will be used to perform dose escalation and MTD/RP2D determination. Briefly, the mTPI-2 method uses a Bayesian framework and a hierarchical model to compute the dose escalation based on the interval between the toxicity rate of each dose level and target probability ([Greenberg 2012](#), [Guo 2017](#)). This study is designed targeting a dose-limiting toxicity (DLT) rate of 20% with an equivalence interval of 15% to 25%.

Like the 3+3 design, the mTPI-2 method incorporates prespecified escalation rules that can be presented in a table ([Table 5](#)). As shown in [Table 5](#), the number of patients dosed at a given dose level are shown in the columns, while the rows indicate the number of DLTs experienced. The escalation/de-escalation rules from the table will be used for each dose level evaluated; the patient numbers and DLTs do not carry over from cohort to cohort. As an example, within a cohort:

- If none of the 3 patients experience a DLT → escalate the dose (“E” at column 3 row 0) to the next dose level cohort.
- If 1 out of 3 patients experience a DLT → de-escalate to a lower dose level (“D” at column 3 row 1).
- If 2 out of 3 patients experience a DLT → the dose is determined to be unacceptably toxic and will not be used again, de-escalate to a lower dose level (“DU” at column 3 row 2).
- If 1 out of 5 patients experience a DLT → stay at the same dose level (“S” at column 5 row 1).

The following rules apply during dose escalation:

- Starting dose at Cohort 1 is **100** mg.
- Although in the mTPI-2 method the cohort size is not fixed, at least 3 patients will be enrolled at each dose level. When all patients at a dose level complete DLT assessment, the study will escalate to the next dose level and another minimum of 3 patients will be recruited in this order until RP2D or MTD ([Table 5](#)).
- The sample size of a dose cohort that has already passed the preliminary DLT assessment (3 to 6 patients) and shown efficacy (eg, to include other efficacy signal for each tumor type) can be extended to 12 patients in order to further evaluate the safety and efficacy signals of that particular dose.

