6.1.10.2 Hematology – Blood Transfusion History and Blood Transfusion Record

Blood transfusion history, including red blood cell and/or platelet infusion within 8 weeks prior to HMPL-306 administration, will be recorded during Screening. The type of infusion, number of infusion unit(s), and date of infusion should be recorded. The pre-infusion hemoglobin level and/or platelet count should also be recorded if obtainable (either is acceptable, both are not required).

Blood transfusion record will include red blood cell and/or platelet infusion after the start of study drug administration until end of treatment (EOT) visit. The type of infusion, number of infusion unit(s), and date of infusion should be recorded. The pre-infusion hemoglobin level and/or platelet count should also be recorded if obtainable (either is acceptable, both are not required).

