6.1.19 Follow-up Period

Safety Follow-up

All patients who have completed an EOT Visit will have a Safety Follow-up Visit. The Safety Follow-up Visit will be conducted at 30 days (± 7 days) from EOT Visit.

AEs related to the study drug will be followed until resolution and SAEs will be followed until resolution regardless of the relationship to the study drug.

All female patients of childbearing potential must complete a pregnancy test (serum or urine) during the Safety Follow-up Visit. Pregnancy testing should be repeated for patients with suspected pregnancy. This is not applicable for postmenopausal female patients (defined as at least 12 months of amenorrhea without alternative medical cause), and the date of menopause should be recorded instead.

Efficacy Follow-up

Patients who discontinue the study drug due to reasons other than disease progression, death, lost to follow-up, or withdrawal of consent will remain on study for tumor assessments and will be followed every 12 weeks (± 14 days) from the EOT visit or last assessment, until disease progression, initiation of new anticancer therapy, withdrawal of consent, lost to follow-up, death, conditions are met per Section [6.2.1](#), or the end of the study, whichever comes first.

Survival Follow-up

All patients will be followed for survival status every 12 weeks (± 14 days), until death, lost to follow-up, or withdrawal of consent. Survival information can be obtained via phone and information will be documented in the source documents and relevant CRFs.

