5.1.2.2. Concomitant Medication/Procedure/Surgery Start/End Date

Concomitant Medication/Procedure/Surgery with onset/end dates that are partially/completely missing will be imputed as follows.

(i) start date:

- 1st day of the month will be used to impute the start date if only the day is missing
- January 1st will be used to impute the start date if both the day and month are missing
- If the date is completely missing, then the day before the reference start date will be imputed as the start date.

(ii) end date:

- Last day of the month will be used to impute the end date if only the day is missing
- December 31st of the year will be used to impute the end date if both the day and month are missing
- If the date is completely missing, assign ‘continuing’ status to the end date

If the imputed end date is after the death date or last known alive date, the date of the death or last known alive date will be imputed as the Concomitant medication/procedure/surgery end date.

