5.2.9.4. Baseline Transfusion Dependence and Post-baseline Transfusion Independence

For the baseline TD and post-baseline TI defined in [Section 4.2.8](#), the number and percentage of patients in each endpoint will be summarized descriptively. Clopper-Pearson exact method will be used to construct the two-sided 95% exact CIs.

In addition, shift tables between the baseline TD and post-baseline TI will be provided.

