5.2.11.3. Death

Number of deaths and primary cause of death will be summarized descriptively. Similarly, the on-treatment deaths (i.e. deaths happening from first study drug administration to 30 days after the date of last administration of study drug or prior to the start of a subsequent anti-tumor therapy (whichever comes first)) and death during the follow-up period (i.e. deaths happening after 30 days after the date of last administration of study drug or prior to the start of a subsequent anti-tumor therapy (whichever comes first)) will also be tabulated.

All death information will be provided as patient list in which the on-treatment death will be flagged.

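### The transfusion-independence window does not stop at death or last observation, so its 30-day tail alone can make a patient who is still being transfused count as TI-4

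*SAP*

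**What the plan says.** Post-baseline transfusion independence is a listed secondary endpoint (Protocol Table 3, SAP Table 1). SAP 4.2.8 measures it within a treatment period that starts with the first Cycle 1 dose and runs "to 30 days after the last dose date or prior to the start of a subsequent anti-tumor therapy (whichever comes first". Within that window, "Post-baseline TI-4 is defined to have no RBC or platelet transfusion for at least" 4 weeks; TI-8 uses 8 weeks. Each is derived overall, for red cells and for platelets, giving six endpoints.

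SAP 5.2.9.4 reports counts, percentages and Clopper-Pearson intervals, and adds that "shift tables between the baseline TD and post-baseline TI will be provided". It sets no evaluability or minimum follow-up condition. The efficacy set (SAP 3.1.4) is everyone dosed from Cycle 1 Day 1, so early deaths are in the denominator.

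Neither the general treatment period in SAP 4.1.4 nor Protocol 9.2.7 adds an end at death or loss.

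On data collection, Protocol 6.1.10.2 records any red cell or platelet "infusion after the start of study drug administration until end of treatment (EOT) visit". The Schedule of Events (Table 1) appears to continue the record to Safety Follow-up. Protocol 6.1.19 states: "All patients who have completed an EOT Visit will have a Safety Follow-up Visit".

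**The concern.** A person cannot be transfused after death, and the database cannot show a transfusion given after recording stopped. If the window runs on regardless, those days count as transfusion-free. The tail (30 days) is longer than the TI-4 requirement (28 days), so the tail alone is enough.

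The situation is foreseeable. The protocol cites a median overall survival of about 1.5 months in refractory AML (2.3.1 and 4.2.2.1). Treatment must stop at progression (6.2.1.1), and Appendix 8 notes that progression is usually accompanied by a greater need for transfusion. SAP 5.2.11.3 tabulates "on-treatment deaths (i.e. deaths happening from first study drug administration to 30 days after the date of last administration of study drug", so the plan itself expects deaths inside the tail.

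At stake is the reading of the TI tables by dose level. A patient who was transfusion dependent at baseline, was transfused up to the last dose and died days later could appear in the shift table as having become independent.

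**Working it through.** The documents give no expected TI rate or sample size for TI, so there is no figure of the plan's to reproduce. The check applies the stated rule to dates.

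**Notation.** L = day of last dose, T = day of last recorded transfusion, D = day of death, all counted from Cycle 1 Day 1. No subsequent therapy starts before L+30.

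**Inputs.** Window end L+30, TI-4 = 28 days and TI-8 = 56 days (SAP 4.2.8). EOT visit at 7 ± 3 days after the last dose (Protocol 6.1.18). Safety Follow-up at EOT + 30 ± 7 days (Protocol 6.1.19). Dose-level size: "at least 3 patients will be enrolled at each dose level", extendable to 12 (Protocol 4.1.1).

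**Days credited after the last transfusion.** Credited = (L + 30) − T.
- TI-4: (L + 30) − T ≥ 28, so T ≤ L + 2.
- TI-8: (L + 30) − T ≥ 56, so T ≤ L − 26.

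With T = L the tail gives 30 days, or 29 if the end day is excluded. TI-4 is met either way, whatever the date of death.

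**Credited against observed.** Observed = D − T.
- TI-4: transfused every 4 days to L = T = 20, D = 25. Credited 50 − 20 = 30; observed 25 − 20 = 5.
- TI-8: L = 60, T = 34, D = 65. Credited 90 − 34 = 56; observed 65 − 34 = 31.
- Never transfused after Cycle 1 Day 1, a single dose on Day 1, death on Day 5. Credited Days 1 to 31 = 31; observed 5.

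**With the window cut at death.** For a patient transfused weekly up to and including day L, the longest transfusion-free run is:

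| Death at | Longest run (days) | TI-4 |
|---|---|---|
| L+1 | 6 | no |
| L+3 | 6 | no |
| L+7 | 7 | no |
| L+10 | 10 | no |
| L+14 | 14 | no |
| L+27 | 27 | no |
| L+28 | 28 | yes |

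Under the rule as written, every row is TI-4 with 30 days.

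**When recording ends.**
- If Protocol 6.1.10.2 governs, recording stops between L+4 and L+10. Then 30 − 10 = 20 to 30 − 4 = 26 tail days are unrecorded, even in survivors.
- If the schedule governs and the patient attends, Safety Follow-up falls between L + 4 + 23 = L+27 and L + 10 + 37 = L+47. Then 0 to 3 tail days are unrecorded.

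**Effect of one misclassified patient (Clopper-Pearson 95% CI).**

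| Dose level size | Without | With | Shift |
|---|---|---|---|
| 3 | 0/3, 0–70.8% | 1/3, 0.8–90.6% | 33 points |
| 12 | 0/12, 0–26.5% | 1/12, 0.2–38.5% | 8 points |

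**The case against.** The SAP never says that days after death count as transfusion-free. Its other treatment-period definitions also omit death, and a sensible programmer might stop there anyway. SAP 5.1.2 takes an observed-case approach, which points away from crediting unobserved days. The condition in 5.1.2.2, "If the imputed end date is after the death date or last known alive date", concerns imputed dates, and the end of the TI window is not one. The on-treatment death window in 5.2.11.3 shares the end point but starts at first study drug rather than Cycle 1. Misclassification needs several things together: death or loss before about L+28, no recorded transfusion after L+2, and no new therapy first. TI is descriptive, the dose decision rests on DLTs, safety, PK and PD, and deaths and efficacy data are listed by patient. A shift of 33 points is what any single reclassification does in a group of three.

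Much of this is fair. The comparison with 5.1.2.2 is weak, and no error rate or dose decision changes. The implied-stop argument does not stand. SAP 4.2.1 ends the best-response period explicitly at death, withdrawal of consent or loss to follow-up, and the PFS and duration-of-response tables give rules for each. Where the SAP wants such a stop it writes one, and 4.2.8 names two end points and takes the earlier. The observed-case text concerns visit data and safety analyses, so it does not settle TI. Patient listings let a reader find the error but do not correct the tables.

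**Conclusion.** The concern holds. Applied as written, SAP 4.2.8 can classify as TI-4 a patient transfused up to two days after the last dose who then dies, withdraws or is lost. All three TI-4 endpoints can be met from the tail alone. The three TI-8 endpoints cannot, but can be inflated when the last transfusion is at least 26 days before the last dose.

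Extra days can only add independent patients, so the error runs only in the drug's favour. The share of patients affected cannot be computed from the documents; the size is known only per patient and per dose level, as shown above.

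This assumes the rule is programmed literally, no subsequent therapy starts in the tail, and death or last observation comes before about L+28. Patients who attend Safety Follow-up are largely observed if the schedule governs recording. TI is a descriptive secondary endpoint, so sample size and error rates are untouched.

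**What to change.** In SAP 4.2.8, end the window at the earliest of:
- death
- last date of transfusion ascertainment
- study discontinuation
- data cut-off
- start of subsequent anti-tumor therapy
- last dose + 30 days

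State that the 28 or 56 transfusion-free days must lie wholly within that window. Define last transfusion ascertainment, for example as the last visit at which the transfusion record was completed. The last known alive date in SAP 4.1.2 is not a full substitute, because it can come from a survival contact at which transfusions were not recorded.

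Reconcile Protocol 6.1.10.2 with the Schedule of Events on when transfusion recording ends.

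The cost is SAP wording, one new date variable and one changed derivation. TI rates will stay the same or fall.
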